**RO7049389—F. Hoffmann-La Roche Ltd**

35/Protocol YP39406, Version 4

5. Informed of, willing and able to comply with all of the protocol requirements and the investigational nature of the study, and have signed an informed consent form (ICF) in accordance with institutional and regulatory requirements.

#### **4.1.3 Exclusion Criteria**

Study subjects who meet any of the following criteria will be excluded from study entry:

1. Pregnant (positive pregnancy test) or lactating women, and male subjects with partners who are pregnant or lactating.
2. History or symptoms of any clinically significant gastrointestinal, renal, hepatic, broncho-pulmonary, neurological, psychiatric, cardio-vascular, endocrinological, hematological or allergic disease, metabolic disorder, cancer or cirrhosis.
3. Personal history of congenital long QT syndrome or family history of sudden death.
4. History of Gilbert's syndrome.
5. History of having received or currently receiving any systemic anti-neoplastic (including radiation) or immune-modulatory treatment (including systemic oral or inhaled corticosteroids)  $\leq$  6 months prior to the first dose of study drug or the expectation that such treatment will be needed at any time during the study.
6. Subjects who have had significant acute infection, e.g., influenza, local infection, acute gastrointestinal symptoms or any other clinically significant illness within two weeks of dose administration.
7. Any confirmed significant allergic reactions (urticaria or anaphylaxis) against any drug, or multiple drug allergies (non-active hay fever is acceptable).
8. Any clinically significant concomitant diseases or condition that could interfere with, or treatment of which might interfere with, the conduct of the study, or that would, in the opinion of the Investigator, pose an unacceptable risk to the subject in this study.
9. Confirmed (based on the average of three separate resting blood pressure measurements, properly measured with well-maintained equipment, after at least 10 minutes rest) systolic BP greater than 140 or less than 90 mmHg, and diastolic BP greater than 90 or less than 50 mmHg at screening.
10. Clinically relevant ECG abnormalities on screening ECG, e.g.,
  - a) QTcF  $>$  450 msec or  $<$  300 msec
  - b) Notable resting bradycardia (HR  $<$  45 bpm), or HR  $>$  90 bpm.
  - c) ECGs with documented machine errors in the interval duration assessments
  - d) Evidence of atrial fibrillation, atrial flutter, complete bundle branch block, Wolf-Parkinson-White Syndrome, or cardiac pacemaker.
11. ECG with QRS and/or T-wave judged to be unfavorable for a consistently accurate QT measurement (e.g., neuromuscular artifact that cannot be readily eliminated, arrhythmias, indistinct QTS onset, low amplitude T-wave, merged T- and U-waves, prominent U-waves).
12. Creatinine clearance (CrCl)  $\leq$  70 mL/min (using the Cockcroft-Gault formula).

**RO7049389—F. Hoffmann-La Roche Ltd**

36/Protocol YP39406, Version 4

13. Positive test at screening of any of the following: hepatitis A (HAV IgM Ab), hepatitis B (HBsAg), hepatitis C (HCV RNA or HCV Ab) or human immunodeficiency virus 1 and 2 (HIV Ab).
14. Any other clinically significant abnormalities in laboratory test results at screening. In the case of uncertain or questionable results, tests performed during screening may be repeated before randomization to confirm eligibility.
15. Participation in an investigational drug or device study within 90 days prior to screening or more than 4 times per year.
16. Donation or loss of blood over 500 mL within 3 months prior to screening.
17. Positive test for drugs of abuse (including recreational drugs) and/or positive alcohol test at screening or on Day -1.
18. Any suspicion or history of drug and/or alcohol abuse within the last year.
19. History (within 3 months of screening) of alcohol consumption exceeding two standard drinks per day on average (1 standard drink=10 grams of alcohol). Alcohol consumption will be prohibited at least 48 hours before screening, 48 hours before and 48 hours after each dose, and 48 hours before each scheduled visit.
20. Use of >5 cigarettes or equivalent nicotine-containing product per day.
21. Taking any prescribed or over-the-counter medications (including vitamins or herbal remedies) within 2 weeks of first dosing or within 5 times the elimination half-life of the medication prior to first dosing (whichever is longer). Occasional acetaminophen/paracetamol is allowed. Exceptions may be made on a case-by-case basis following discussion and agreement between the Investigator and the Sponsor.
22. Subjects under judicial supervision, guardianship or curatorship.
23. Medical or social conditions that would potentially interfere with the subject's ability to comply with the study visit schedule or the study assessments.

#### **4.2 METHOD OF TREATMENT ASSIGNMENT AND BLINDING**

##### **4.2.1 Method of Blinding**

Randomization numbers will be generated by the Sponsor or its designee.

The study is Investigator-blinded and Subject-blinded. In order to minimize bias in reporting, collecting, and interpreting safety data. Study subjects, Investigator(s), and all individuals in direct contact with study subjects at the investigative site will remain blinded until the completion of the study, except the pharmacist handling the study drug distribution.

The study is Sponsor-open. At the Sponsor side, the Clinical Pharmacologists, the Study Pharmacometrist, the Study Clinical Pharmacology Scientist, the Study Biostatistician, the Statistical Programmer/Data Acquisition Specialist/Clinical Data Programmer, and the individual responsible for PK sample bioanalysis – members of the Sponsor's project and study teams who do not have direct contact with the subjects – will be unblinded to

**RO7049389—F. Hoffmann-La Roche Ltd**

37/Protocol YP39406, Version 4

treatment assignment. Other members of the Sponsor staff may be unblinded at the Clinical Pharmacologist's discretion, if this is considered necessary to optimize data analysis and dose-escalation decision making.

Before each of the dose-escalation decisions, the individual safety, tolerability, and available PK data will be reviewed in a blinded fashion by the Investigator and the Sponsor's clinical team during the Safety Review Meeting. The Investigator may also be unblinded in mutual agreement with the Clinical Pharmacologist if treatment assignment knowledge is considered critical to allow study progression, and/or is deemed important to define future risk management activities. Unblinding can occur as soon as the Investigator(s) and the responsible Roche scientists have reviewed the data, even if the data have not been entered onto the Case Report Forms (CRFs). If required, unblinded data (individual as well as at group level) may also be presented to the Drug Safety Committee or other experts of the Sponsor.

As per Health Authority reporting requirements, the Sponsor will break the treatment code for all unexpected serious adverse events (SAE; see Section 5.2.1) that are considered by the Investigator to be related to study drug.

All such occurrences should be documented in the study file. Treatment codes should not be broken except in emergency situations and, if possible, the responsible scientific leader should be contacted before the code is opened. At the final monitoring visit, the unused treatment codes will be counted and checked and a statement to the effect that all are intact (or not as the case may be) will be made by the monitor; this statement will be included or referred to in the final study report. All treatment codes will be returned to Roche.

Whenever disclosure of the identity of the test medication is necessary, adequate procedures will be in place to ensure integrity of the data. Any unblinding will be documented in the study report with date, reason for identifying the drug and the name(s) and role(s) in the study of the person(s) unblinded.

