## **5.2 METHODS AND TIMING FOR CAPTURING AND ASSESSING SAFETY PARAMETERS**

The Investigator is responsible for ensuring that all adverse events (see Section 5.1.1 for definition) are recorded on the Adverse Event eCRF and reported to the Sponsor in accordance with instructions provided in this section and in Sections 5.3, 5.4, and 5.5.

For each adverse event recorded on the Adverse Event eCRF, the Investigator will make an assessment of seriousness (see Section 5.1.2 for seriousness criteria), severity (see Section 5.2.3), and causality (see Section 5.2.4).

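### Section 4.2.1 allows a non-emergency unblinding of the Investigator before adverse event ratings have been fixed

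*Combined protocol and SAP*

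**What the plan says.** Section 4.2.1 keeps subjects, Investigators and site staff blinded to the end of the study, apart from the dispensing pharmacist. The stated aim is "In order to minimize bias in reporting, collecting, and interpreting safety data".

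The section then describes the step before each dose escalation. Individual safety, tolerability and available PK data are "reviewed in a blinded fashion by the Investigator" and the sponsor's clinical team. After that comes a discretionary route, open to one named role on the sponsor's side and the site: "The Investigator may also be unblinded in mutual agreement with the Clinical Pharmacologist". Two grounds are given for using it, and the condition reads "if treatment assignment knowledge is considered critical to allow study progression, and/or is deemed important to define future risk management activities". On timing, it may happen once the Investigator and the sponsor's scientists have "reviewed the data, even if the data have not been entered onto the Case Report Forms (CRFs").

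Later in the same section: "Treatment codes should not be broken except in emergency situations". Any unblinding is to be documented in the study report with its date, its reason and the people involved, and suitable procedures to protect data integrity are promised but not described.

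Section 5.2 says who makes the ratings: "For each adverse event recorded on the Adverse Event eCRF, the Investigator will make an assessment of seriousness", together with severity and causality.

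**The concern.** The protocol blinds the Investigator so that knowledge of treatment cannot affect how safety data are reported and collected. The discretionary route permits that knowledge at a point when some of the reporting may still be undone. The primary objective is safety and tolerability compared with placebo, and the first safety outcome measure is the incidence and severity of AEs. Both depend partly on the Investigator's judgement. So do the escalation criteria in section 3.1.2.1, which turn on whether events are drug-related and clinically significant. If those judgements can be entered or altered with the allocation in view, the protection is lost for the cohort concerned, and the analysis section does not say how such entries would be treated.

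**Working it through.** This is a check of text; no formula decides it. The one probability in the plan reproduces: section 6.1 gives 94% for seeing at least one AE of 25% incidence among ten active subjects, and 1 − 0.75^10 = 1 − 0.0563 = 0.9437. It has no bearing on this point.

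1. **Reasons for unblinding (4.2.1).** Study progression or future risk management. Neither is an emergency.
2. **Timing (4.2.1).** After the data have been reviewed, and expressly without waiting for CRF entry.
3. **What is fixed by then.** Sections 3.1.2 and 4.2.1 require a review and an agreed escalation decision. Neither asks for AE ratings to be written down, signed or locked. Section 5.2.1 has AEs noted in the medical record before they go onto the eCRF, but does not say that severity and causality are noted there.
4. **What is still open to judgement.** Causality is a yes/no decision by the Investigator (5.2.4). A laboratory or vital-sign change can become an AE on the Investigator's view of clinical significance alone (5.2.5.4, 5.2.5.5). Severity is updated when an event worsens (5.2.5.3). For serious AEs and AEs of special interest, a changed causality is accepted as follow-up information (5.3).
5. **Where each judgement goes.**

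| Judgement | AE tables (6.5.1) | Escalation criteria (3.1.2.1) |
|---|---|---|
| Laboratory or vital-sign change reported as an AE | Yes, incidence | Significance and relatedness are judged there too |
| Severity | Yes, maximum severity and severe versus non-severe | Yes, for the AE criterion |
| Causality | No relatedness table is planned | Yes |

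6. **Scale of one changed entry.** Cohorts 2 to 4 have 10 active subjects each, so one subject who changes category moves a proportion by 1/10 = 10 percentage points. Pooled placebo in the SAD phase is 2 + 2×2 = 6 subjects without the optional Cohort 4, or 2 + 2×3 = 8 with it, so one subject there is 1/6 = 16.7 or 1/8 = 12.5 points. These are step sizes, not estimates of bias.

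**The case against.** The case against is substantial and narrows the point.

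- **Unblinding is conditional and comes after a blinded review.** It needs agreement between two parties and a stated kind of reason, and may never be used. The Investigator will have seen the data blinded first. This stands, but a review that leaves no signed rating does not fix one.
- **Serious AEs and AEs of special interest are largely protected.** Section 5.3 requires them to be reported within 24 hours, so their first ratings will usually precede any unblinding. A reader might infer that the halt for a related serious AE is readily exposed; the reporting rule makes that link weak. The gap is mainly in ordinary AEs.
- **Much of the safety record does not depend on a rating.** Laboratory values are flagged against sponsor reference ranges (6.5.2), and vital signs and ECGs are listed and summarized in their own right (6.5.3, 6.5.4). Severity in Table 2 is defined by effect on daily activity, which leaves less room than causality does. The sponsor also makes its own unblinded review before each escalation (3.1.2.1).
- **Data not yet on the CRF may still be recorded.** Source notes come first. That is fair, but the protocol does not require the ratings to be in them.
- **Late entries can be traced.** The eCRF audit trail (7.2) and the dated unblinding record allow entries made afterwards to be identified. They do not prevent them, and section 6 makes no use of them.
- **The emergency-only sentence may concern something else.** It stands next to the counting and return of unused treatment codes and can be read as governing code breaks at the site. It is therefore weak evidence of a contradiction, though the section should say which reading is meant.

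**Conclusion.** The point holds as a gap that is cheap to close. After a blinded review, section 4.2.1 permits a non-emergency unblinding of the Investigator before the reviewed data are on the CRFs, and no section requires AE ratings to be fixed first. For ordinary AEs in that cohort, the decision to report a laboratory or vital-sign change as an AE, its severity and its causality could be made or revised with treatment known. That is contrary to the section's own purpose.

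The size and direction of any effect are unknown. It arises only if the discretionary route is used and the ratings have not in practice been written down beforehand; the documents settle neither.

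Two stronger readings are tempting and are not supported. A reader might infer that the planned comparison with placebo would show a biased rate of related events. Section 6.5.1 lists no summary by relatedness, and section 5.2.1 collects AEs after first dosing whatever their relationship to treatment, so causality matters through the escalation criteria instead. A reader might also try to calculate how much likelier an escalation stop becomes, by assuming background and attribution rates and counting three or more related events among ten active subjects. The AE criterion asks for more than two active subjects with events that are severe, clinically significant, related and alike in kind; the laboratory, vital-sign and ECG criteria likewise require clinical significance, relatedness and likeness. A count of any related events is a different quantity, and the documents give no attribution rates.

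**What to change.** In section 4.2.1, amend the sentence that begins "Unblinding can occur as soon as the Investigator(s) and the responsible Roche scientists have reviewed the data, even if the data have not been entered". Replace its concession about data entry with a requirement that, except in a medical emergency, AE terms, seriousness, severity and causality to date for that cohort are recorded, dated and signed by the Investigator, in the eCRF or on a source form, before the Investigator is unblinded.

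Add to section 6.5.1 that entries or changes made after unblinding, including severity updates under section 5.2.5.3, continue and remain in the AE tables, but are flagged in the listings with any pre-unblinding rating shown alongside. Restricting the tables to the blinded rating would be wrong here: it would leave out genuine later worsening and conflict with tabulating maximum severity.

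Reconcile the discretionary route with the statement that Investigators stay blinded to the end of the study, and with the emergency-only sentence on treatment codes.

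The signed rating protects only the record to date. Section 3.1.1.2 keeps the same allocation in the MAD phase, so after an unblinding at the end of the SAD phase, new events in continuing subjects would be rated with treatment known. The flag makes these visible but does not prevent it.

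The cost is an edit to one sentence, a listing flag that can draw on the existing audit trail and unblinding record, and a short delay before a discretionary unblinding. The delay is assumed to be hours to about a day; the documents give no figure. No dosing or stopping rule changes.

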#### **4.3 STUDY TREATMENT**

##### **4.3.1 Formulation, Packaging, and Handling**

###### **4.3.1.1 RO7049389 and Placebo**

RO7049389 and matching placebo (IMP) to be used in the study will be provided by Roche.

**RO7049389—F. Hoffmann-La Roche Ltd**  
38/Protocol YP39406, Version 4

A matching-placebo, in terms of size, shape and color, has also been developed for clinical usage.

Film-coated tablets of RO7049389 should be stored under the recommended storage conditions "Store at 2-8°C, protect from light and moisture". For information on the shelf-life of RO7049389 film-coated tablets and the respective placebos, see the packaging.

Study drug packaging will be overseen by the Roche clinical trial supplies department and bear a label with the identification required by local law, the protocol number, drug identification and dosage. The packaging and labeling of the study drug will be in accordance with Roche standard and local regulations.

Upon arrival of investigational products at the site, site personnel should check them for damage and verify proper identity, quantity, integrity of seals and temperature conditions, and report any deviations or product complaints to the Monitor upon discovery.

For further details, see the [Investigator's Brochure](#).

#### **4.3.2 Dosage, Administration and Compliance**

##### **4.3.2.1 RO7049389 and Placebo**

The health care professionals at the study site administering the study drug to the subject must check to be sure that the study drug is swallowed.

The qualified pharmacist at the pharmacy will keep drug accountability and record the study drug batch or lot number received by each subject during the study.

Accountability and subject compliance will be assessed by maintaining adequate study drug dispensing records. The Investigator is responsible for ensuring that dosing is administered in compliance with the protocol. Delegation of this task must be clearly documented and approved by the Investigator.

Active or placebo doses will be administered orally to the study subjects with approximately 240 mL of still water at room temperature. An additional amount of water up to 100 mL can be given to assist dose administration only if needed. The dose in mg, the date and time of dosing, and the exact volume of water should be recorded on the eCRF (the exact volume of water consumed during dose administration will be recorded during the in-clinic period).

The qualified individual responsible for dispensing the study drug will prepare the correct dose according to the randomization schedule. This individual will write the date dispensed and study subject's number and initials on the study drug vial label and on the Drug Accountability Record. This individual will also record the study drug batch or lot number received by each study subject during the study.

Guidelines for dosage modification and treatment interruption or discontinuation are provided in Section 3.1.2.

#### **SAD Phase**

RO7049389 or matching-placebo will be administered orally with 240 mL of water to the healthy subjects by investigational staff in the morning of Day 1 after an overnight fast of at least 8 hours.

Healthy volunteers will not eat for at least 4 hours after the dose is administered. Water will be allowed until one hour prior to dosing, and from one hour post-dosing. Approximately 4-5 hours after dosing, healthy subjects will be served lunch.

#### **MAD Phase**

RO7049389 or matching-placebo will be administered orally with 240 mL of water to the healthy subjects by investigational staff from Day 1 through to Day 13 q12h, and on Day 14 once in the morning.

*Except for cohort 4, which will be in the fasted state,* a standard breakfast or dinner will be served to healthy volunteers 30 minutes prior to dosing, which should be consumed within 30 minutes. RO7049389 or placebo will then be administered.

Lunch will be served approximately 4-5 hours post-morning-dose. The second daily dose will be administered in the evening, approximately 12 hours after the morning dose.

Timing of meals relative to dosing may be changed according to emerging data.

Guidelines for dietary stipulations are provided in Section 4.4.3 and Section 4.4.4.

#### **4.3.3 Investigational Medicinal Product Accountability**

All investigational medicinal products (IMPs) required for completion of this study (RO7049389 and matching-placebo) will be provided by the Sponsor. The investigational site will acknowledge receipt of IMPs, to confirm the shipment condition and content. Any damaged shipments will be replaced.

The Investigator is responsible for the control of drugs under investigation. Adequate records of the receipt (e.g., Drug Receipt Record) and disposition (e.g., Drug Dispensing

**RO7049389—F. Hoffmann-La Roche Ltd**  
40/Protocol YP39406, Version 4

Log) of the study drug must be maintained. The Drug Dispensing Log must be kept current and should contain the following information:

- The identification of the study subject to whom the study drug was dispensed (for example, study subject initials and date of birth).
- The date(s), quantity of the study drug dispensed to the study subject.
- The identification of the person who dispensed the drug.
- All records and drug supplies must be available for inspection by the Clinical Trial Monitor at every monitoring visit.

IMPs will either be disposed of at the study site according to the study site's institutional standard operating procedure or returned to the Sponsor with the appropriate documentation. The site's method of IMP destruction must be agreed upon by the Sponsor. Local or institutional regulations may require immediate destruction of used investigational medicinal product for safety reasons. In these cases, it may be acceptable for investigational study site staff to destroy dispensed investigational product before a monitoring inspection provided that source document verification is performed on the remaining inventory and reconciled against the documentation of quantity shipped, dispensed, returned, destroyed and provided that adequate storage and integrity of drug has been confirmed.

The site must obtain written authorization from the Sponsor before any IMP is destroyed, and IMP destruction must be documented on the appropriate form.

Written documentation of destruction must contain the following:

- Identity of investigational product(s) destroyed
- Quantity of investigational product(s) destroyed
- Date of destruction
- Method of destruction
- Name and signature of responsible person [or company] who destroyed investigational product[s]

Accurate records of all IMPs received at, dispensed from, returned to, and disposed of by the study site should be recorded on the Drug Inventory Log.

